10.1.2 Statistical analyses overview

Descriptive statistics will be calculated for all variables, including mean, median, standard deviation and range for numerical variables and absolute and relative frequencies for categorical variables. Whenever relevant, 95% confidence intervals (CI) will be computed. For each study endpoint, data will be summarized by IBD type (CD and UC).

Cross-sectional analysis

The cross-sectional analysis will be conducted once all patients have completed the Day 1 assessment (expected to occur 6 months after start of enrolment).

This analysis will allow a characterization of the study population, the estimation of primary endpoints and to compare the subgroup of patients with no or light activity of disease and those with moderate to severe activity. Hence, for each IBD type, the patients with disease activity will be compared with patients with no or light activity regarding socio-demographic, clinical and treatment variables of interest. Chi-square or Fisher exact tests will be used to compare activity vs non-activity regarding qualitative variables and t-student / Mann-Whitney tests will be used for comparison of quantitative variables. If applicable, logistic regression will be used for evaluating associated variables. All tests will be two-sided considering a significance level of 5%.

Longitudinal analysis

The longitudinal analysis will be performed once all the patients that were included in the prospective period have completed the 12-month follow up.

The proportion of controlled patients will be presented as well as the 95%CI at the 12-month follow up assessment. If applicable, logistic regression will be used for calculating odd ratios and 95% confidence intervals for the patient control at month 12 determined by independent variables. All tests will be two-sided considering a significance level of 5%.

In case the expected ratio of IBDs (50%CD/50%UC) is not attained at 2 and 4 months of enrolment, the participating sites will be instructed to change future enrolments so that this balance is achieved and that at least 30 UC patients and 30 CD patients with active disease enter the prospective follow-up.

For details of the statistical analyses please refer to the Statistical Analysis Plan.

10.2 Primary Analyses

For Crohn's Disease (CD), the proportion of patients with active disease at Day 1 will be presented as percentage and calculated as:

$$\frac{CD \text{ patients with } HBI \geq 8 \text{ or } CDAI > 220}{Total \text{ CD patients}} \times 100$$

For Ulcerative Colitis (UC), the proportion of patients with active disease at Day 1 will be presented as percentage and calculated as:

$$\frac{UC \text{ patients with partial Mayo score} \geq 5}{Total \text{ UC patients}} \times 100$$

The 95% confidence intervals will be computed for each estimate.

10.3 Secondary Analyses

At the cross-sectional analysis, the following objectives will be addressed for all IBD patients:

- In order to characterize socio-demographic and clinical aspects of moderate to severe IBD, a summary table with the descriptive statistics of the selected variables, by CD and UC patients.
- Descriptive statistics will also be used to summarize treatment patterns for CD and UC in the previous 3 years, including the use of biologic therapies and failure to these therapies (if any), time between IBD diagnosis and initial treatment, first treatment after diagnosis of moderate to severe IBD, among other variables of interest.
- Within CD and UC groups, the patients with moderate to severe disease activity will be compared with patients with no or light activity, regarding socio-demographic, clinical and treatment variables of interest:
 - Chi-square or Fisher exact tests will be used to compare qualitative variables, such as gender, smoking habits, professional status, family history of IBD, steroid behavior (dependent/refractory), previous treatment with biologic therapies, and previous surgery for IBD, among others.

- The t-student or Mann-Whitney tests will be used for comparison of quantitative variables, such as age, time since diagnosis, and duration of treatment, among others.
- If applicable, logistic regression models (for CD and UC patients) will be used to identify independent variables associated with disease control at Day 1, and odds ratios (OR) with 95% CI will be presented.
- Within CD and UC groups, the patients with moderate to severe disease activity will be compared with patients with no or light activity, regarding socio-demographic, clinical and treatment variables of interest.
- For each IBD disease, descriptive statistics – mean, standard-deviation (SD), median, minimum, maximum – will be used to summarize patients' quality of life, overall and according to disease activity
 - The score of EQ-5D analog scale and responses to each item.
 - Utilities will be configured such that 0.0 is associated with being dead and 1.0 is associated with perfect health; thus, a higher utility value is considered better. Mean (SD) utility index will be estimated for CD and UC patients, overall and according to disease activity.
 - The SF-36 uses 36 items to evaluate eight health dimensions:
 - Physical Functioning (raw score) - sum of Q3a, Q3b, Q3c, Q3d, Q3e, Q3f, Q3g, Q3h, Q3i, Q3j
 - Role Physical (raw score) - sum of Q4a, Q4b, Q4c, Q4d
 - Body Pain (raw score) - sum of Q7, Q8
 - General Health (raw score) - sum of Q1, Q11a, Q11b, Q11c, Q11d
 - Vitality (raw score) - sum of Q9a, Q9e, Q9g, Q9i
 - Social Functioning (raw score) - sum of Q6, Q10
 - Role-Emotional (raw score) - sum of Q5a, Q5b, Q5c
 - Mental Health (raw score) - sum of Q9b, Q9c, Q9d, Q9f, Q9h
 - Based on SF-36 standardized scores, two summary scores are estimated, the Physical Component Score and the Mental Component Score
 - The IBDQ score and each of the four IBDQ domains:
 - Bowel function – sum of questions 01, 05, 09, 13, 17, 20, 22, 24, 26, 29.
 - Emotional status – sum of questions 03, 07, 11, 15, 19, 21, 23, 25, 27, 30, 31, 32.
 - Systemic symptoms – sum of questions 02, 06, 10, 14, 18.

- Social function – sum of questions 04, 08, 12, 16, 28.
- To evaluate the work productivity impairment (WPAI) experienced by moderate to severe IBD patients, the following variables will be estimated and summarized, by CD or UC, overall and according to disease activity:
 - In brief, the WPAI questions are: 1) if currently employed, 2) hours missed due to disease, 3) hours missed other reasons, 4) hours actually worked, 5) degree disease affected productivity while working, 6) degree disease affected regular activities.
 - Mean (SD) total work productivity impairment (TWPI), defined as the mean of subjects total percentage of work impairment associated with IBD that results from both absenteeism and presenteeism, and assessed with specific WPAI for each IBD type. The TWPI due to IBD will be calculated as
$$Q2/(Q2+Q4)+[(1(Q2/(Q2+Q4)))x(Q5/10)]*100$$
 - Mean (SD) work time missed due to IBD. The percentage of work time missed due to IBD will be calculated for each subject as $Q2/(Q2+Q4)*100$
 - Mean (SD) impairment while working due to IBD. The percentage of impairment while working due to IBD will be calculated for each subject as $Q5/10*100$
 - Mean (SD) total activity impairment due to IBD. The percentage of total activity impairment due to IBD will be calculated for each subject as $Q6/10 *100$
 - Additionally, the proportions of patients reporting some absenteeism, some work impairment, and some activity impairment due to IBD will be presented.
- Health resources (previous 3 years) will be described by IBD group and by disease activity, for the following events: drug therapies, number and type of imaging and laboratory testing, surgeries, number, reason and duration of hospitalizations, number and type of consultations with gastroenterologists or other medical specialists and adverse events.
- Health Care Resource Costs
Costs will be reported in total and on a per patient per month basis. Costs will be obtained by multiplying resource use with relevant unit costs. Unit costs for resource items will be collected by in Brazilian reliable administrative databases or other sources.

UC or CD-related health care costs. Consumer price index (CPI)-adjusted IBD-related health care costs will be computed as total costs, medical costs, drug costs, and other costs.

Treatment pattern costs. Treatment pattern costs will be calculated as total UC or CD-related health care costs, stratified by the defined treatment patterns.

In addition to the descriptive cost data, multivariate cost models may be developed where the observation time is divided into intervals of equal length.

For patients with active IBD at study appointment (Day 1), and included in the prospective period, the following analysis will be conducted:

- Descriptive statistics will be presented in a summary table, for the main socio-demographics, clinical characteristics and treatment regimen of the included patients at Day 1 (baseline), by IBD disease.
- The proportion of patients with active CD after 12 months among patients who had moderately to severely active CD at Day 1 (baseline) will be expressed as percentage and determined as

$$\frac{CD \text{ patients with } HBI \geq 8 \text{ or } CDAI > 220 \text{ after 12 months}}{Total \text{ CD patients with } HBI \geq 8 \text{ or } CDAI > 220 \text{ at Day 1}} \times 100$$

- Similarly, the proportion of patients with active UC after 12 months among those who had moderately to severely active UC at Day 1 (baseline) will be expressed as percentage and determined as:

$$\frac{UC \text{ patients with partial Mayo score } \geq 5 \text{ after 12 months}}{Total \text{ UC patients with partial Mayo score } \geq 5 \text{ at Day 1}} \times 100$$

- Patients that had light or no activity of disease at the end of the 12-month follow-up will be compared with patients that remained with active disease, regarding socio-demographic, clinical and treatment variables of interest. Similarly to the cross-sectional analysis, the comparison of categorical variables will be conducted with Chi-square or Fisher exact tests and t-student or Mann-Whitney tests will be used to compare quantitative variables.
- If applicable, variables associated with having light or no activity 12 months after baseline will be identified through logistic regression models for each IBD disease and OR (95%CI) will be presented.

- In addition, survival analysis with Kaplan Meier curves and Cox regression models will be used (if applicable) to identify factors associated with achieving light or no activity with baseline treatment (continued or initiated at baseline), during follow-up. In this analysis, patients that remained with active disease or that change treatment due to lack of disease control will be censored and, conversely, success will be defined as having light or no active disease. Time to success will be considered as dependent variable in survival analysis methods.
- The number and reason for treatment changes during follow-up will be summarized and treatment patterns during prospective period will also be described. Patients with treatment changes will be compared with those without changes, regarding main socio-demographic, clinical and treatment baseline variables. The comparison of categorical variables will be conducted with Chi-square or Fisher exact tests and t-student or Mann-Whitney tests will be used to compare quantitative variables.
- If applicable, Poisson regression models based on generalized linear equations will be used to examine the relationship between variables of interest and the incidence of the treatment changes during follow-up.

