The Inflammatory Bowel Disease Questionnaire (IBDQ) is a 32-item questionnaire that measures 4 dimensions: bowel function, emotional status, systemic symptoms, and social function. Within dimensions, each question presents seven possible answers/points. The score for each dimension results from the sum of points. Hence, the total score ranges from 32 to 224, with higher scores representing better quality of life (34). A Portuguese (Brazil) version was already validated (35). The IBDQ is not validated for patients with ostomies and therefore should not be applied for these patients. For more information, please consult <http://www.flintbox.com/public/project/641>.

The Work Productivity and Activity Impairment questionnaire (WPAI) assesses the impact of IBD on work productivity and daily activities during the previous 7 days. In brief, the WPAI questions are: 1) if currently employed, 2) hours missed due to disease, 3) hours missed other reasons, 4) hours actually worked, 5) degree disease affected productivity while working, 6) degree disease affected regular activities (7). WPAI generates four component scores: percentage of work time missed (absenteeism); percentage of impairment while working (presenteeism); percentage of overall work impairment (absenteeism and presenteeism combined); and percentage of activity impairment. Unemployed patients only answer to questions related to employment status and activity impairment. Scores for WPAI range from 0% ('no impairment') to 100% ('total loss of work productivity/activity'). For more information, please consult http://www.reillyassociates.net/WPAI_General.html.

Treatment

- Previous treatments or regimens (aminosalicylates, steroids, immunomodulators, immunosuppressors, biologics, probiotics, antibiotics); start date; end date, dose, reason for discontinuation;
- Treatment started at Day 1 (name, dose);
- Previous surgeries for IBD.

At follow up appointment only:

- Therapeutic strategy: maintain current treatment vs discontinued;
- If discontinued, new treatment (name, dose, start date), and reason for discontinuation.

Other health care resources related with IBD management

- Imaging and laboratory testing;
- Surgeries;
- Hospitalizations;
- Consultations;
- Adverse Events.

8 Management and Reporting of Adverse Events

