## 7.7 Missing data

Missing values will not be replaced in this study.

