For cross-sectional analysis dataset, the comparison of SF-36 scale scores or component summary scores, EQ-5D VAS scale and IBDQ domain scores or total score according to disease activity will be performed through the t-test for independent samples or Mann-Whitney test in case of non-normality of the quantitative variable distribution. The association between each EQ-5D dimension and disease activity will be determined for each IBD type using Chi-Square Test. If applicable, if the number of patients in the levels of each dimension is small, the severity of each dimension will correspond to: have problems (group moderate, severe and unable/extreme problems) and have no problems (group slight or no problems). The correlation of scales scores of IBDQ and EQ-5D dimensions or VAS scale with SF-36 scales scores will be determined for each IBD type using Pearson or non-parametric Spearman's correlation coefficient.

Also for cross-sectional dataset, patients with moderate to severe disease will be compared with patients with no or mild disease regarding WPAI data (percent total work productivity impairment due to IBD, percent work time missed due to IBD, percent impairment while working due to IBD and percent total activity impairment due to IBD) through the t-test for independent samples or Mann-Whitney test in case of non-normality of the quantitative variable distribution.

- 6) Other analysis: The influence of demographic characteristics, comorbidities and extra-intestinal manifestations on the quality of life will be assessed. For each type of IBD, a comparison of patients using biologic treatment and patients who not use biologic treatment regarding quality of life data will be done. Same analysis will be performed for patients who were hospitalized and patients who were not hospitalized.  
IBD treatment-related procedures in the previous 3 years will be described for patients using biologic treatment and patients who not use biologic treatment.

Note: Regions variable should be considered as independent variable for the regression analysis.

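### Total work impairment has no visible rule for an employed patient who worked no hours; if Q5 is blank, a patient at 100% drops out of the mean

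*Protocol*

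**What the plan says.** Protocol 10.3 defines the endpoint as a per-patient percentage, averaged: "defined as the mean of subjects total percentage of work impairment associated with IBD that results from both absenteeism and presenteeism". The printed formula is "Q2/(Q2+Q4)+[(1(Q2/(Q2+Q4)))x(Q5/10)]*100". Absenteeism has its own formula, which does not use Q5: "The percentage of work time missed due to IBD will be calculated for each subject as $Q2/(Q2+Q4)*100".

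Protocol 7.2 describes the items. Q2 is hours missed because of the disease, and the next two that matter are "4) hours actually worked, 5) degree disease affected productivity while working". The only skip instruction is for patients without a job: "Unemployed patients only answer to questions related to employment status and activity impairment". Nothing visible covers an employed patient with no hours worked.

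On missing data, Protocol 10.5 rules out imputation except where the SAP sets out something for the patient-reported tools. SAP 7.7 sets out nothing of the kind: "Missing values will not be replaced in this study".

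Mean total work impairment is a listed endpoint (Protocol 10.1.1; SAP 5.2, health economics). It is summarised overall and by disease activity, and SAP section 8, item 5, adds a test: "patients with moderate to severe disease will be compared with patients with no or mild disease regarding WPAI data".

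**The concern.** The patient who was off work all week because of IBD is the most impaired employed patient the questionnaire can describe. Total impairment for that patient is fixed by the hours alone, but the formula still calls for Q5, an item about time at work that did not occur. If Q5 is blank, the visible rules taken together discard a value that is already known.

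Such a loss would be informative. Whether a patient is dropped would depend on the outcome itself, and every dropped patient would sit at the top of the scale. The absenteeism mean and the total-impairment mean would then describe different sets of employed patients, with the difference confined to those at 100%. A reader comparing the two summaries would not know this.

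**Working it through.** **Reading of the formula.** Write A = Q2/(Q2+Q4) and P = Q5/10. I read the total as [A + (1 - A) x P] x 100, which matches the 0% to 100% range that Protocol 7.2 gives for WPAI scores. The minus sign is absent from the extracted text and may have been lost in reading the PDF, so I make nothing of it. As printed, the x 100 follows the bracket only; that is a separate matter of notation. The documents report no total-impairment result, so there is no figure to reproduce.

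**The fully absent patient.** Take Q2 = 40 and Q4 = 0 as an illustration:

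- A = 40/(40 + 0) = 1, so absenteeism = 100%.
- The weight on Q5 is 1 - A = 0.
- With Q5 = 0, 5 or 10, the total is [1 + 0 x P] x 100 = 100%.
- With Q5 blank, the total is 1 + 0 x missing. Evaluated literally in SAS, the named software, this is missing.

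The value is therefore known in every case, and it is lost only when Q5 is blank and the expression is coded as it stands.

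**A different patient.** If Q2 = 0 and Q4 = 0, for example a week missed wholly for other reasons, A is 0/0. Absenteeism and total impairment are both undefined, and no rule can supply them.

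**Size of the shift in the mean.** Let f be the fully absent share of employed patients and m the mean total impairment of the rest.

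- Mean with everyone: f x 100 + (1 - f) x m
- Mean after the loss: m
- Shortfall: f x (100 - m)

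Neither f nor m is in the documents. Over an assumed range:

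| f | shortfall at m = 40 | shortfall at m = 20 |
|---|---|---|
| 2% | 0.02 x 60 = 1.2 | 0.02 x 80 = 1.6 |
| 5% | 0.05 x 60 = 3.0 | 0.05 x 80 = 4.0 |
| 10% | 0.10 x 60 = 6.0 | 0.10 x 80 = 8.0 |

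**Active versus non-active difference.** Assume the remaining patients average 40 in the active group and 20 in the non-active group, so the difference reported after the loss is 40 - 20 = 20.

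- Fully absent 10% active, 2% non-active: means with everyone are 0.90 x 40 + 10 = 46.0 and 0.98 x 20 + 2 = 21.6. The difference is 24.4, so 20 understates it.
- Fully absent 5% in each: means are 0.95 x 40 + 5 = 43 and 0.95 x 20 + 5 = 24. The difference is 19, so 20 overstates it.

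With these means, the difference is understated only if 60 x f(active) exceeds 80 x f(non-active), that is, if the non-active share is below 60/80 = 75% of the active share.

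**The case against.** A reader might infer that the formula cannot score any fully absent patient. It can: a recorded Q5 of any value gives 100%. The documents do not say whether such a patient skips Q5, and the questionnaire and eCRF are not available. This stands, and it makes the point conditional on blank Q5 values.

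The rule may already exist. The WPAI formulas in SAP 7.6 are redacted, and the derived-variables appendix listed in the SAP contents is not in the supplied text. Protocol 10.5 sends handling of the patient-reported tools to the SAP. This also stands: the plan cannot be said to lack the rule, only that no visible text contains it.

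SAP 7.7 can fairly be read as a ban on imputation, which does not forbid setting a value that follows from the hours. That is right, and it is why the remedy does not conflict with 7.7. But 7.7 does not tell the programmer to set that value either, and the formula run literally does not.

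The share affected may be small. Patients are recruited at scheduled outpatient appointments (Protocol 6.3.4), and those hospitalised at Day 1 are excluded (Protocol 6.3.2). Fully absent patients would also remain in the absenteeism mean and, through Q6, in the activity-impairment mean. This limits the damage to one secondary summary and its comparison by activity; it does not remove it.

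Finally, a reader might infer that the active versus non-active difference must be understated. The second example under the working shows the opposite, so no direction can be claimed.

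**Conclusion.** The point holds in conditional form. Where an employed patient has Q2>0, Q4=0 and a blank Q5, the visible rules followed literally drop a patient whose total is 100% by algebra. For the mean total impairment the direction is certain: downward, by f x (100 - m). The size is not known; about 1 to 8 points rests on assumed values of f (2% to 10%) and m (20 to 40). The direction for the comparison by disease activity is not established. Primary endpoints are unaffected. Confidence is moderate, because the SAP text where a scoring rule would stand cannot be seen. The derivation should still be settled, since the rule is nearly free and changes nothing for patients whose Q5 is recorded.

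**What to change.** Add to the WPAI derivation in the SAP:

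- If Q2>0 and Q4=0, total work impairment = 100% regardless of Q5, and presenteeism is not applicable.
- If Q2+Q4=0, absenteeism and total work impairment are not evaluable.
- Report the number of employed patients in each case, by IBD type and activity group.

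Describe the first rule as a logical derivation, so that it is not read as an exception to SAP 7.7. If the derived-variables appendix already contains it, confirm that and align the formula in Protocol 10.3. The cost is two lines of text, one programming rule and a row of counts in the WPAI tables. No new data are needed.

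### The protocol's formula for WPAI total work impairment scales only its second term by 100, so absenteeism enters as a 0–1 fraction and almost drops out

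*Protocol*

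**What the plan says.** Protocol section 10.3, in the WPAI item, defines TWPI as the mean across subjects of the "total percentage of work impairment associated with IBD that results from both absenteeism and presenteeism". It then gives the calculation as "Q2/(Q2+Q4)+[(1(Q2/(Q2+Q4)))x(Q5/10)]*100".

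The next two items in the same section put each component on the percentage scale. For absenteeism, "The percentage of work time missed due to IBD will be calculated for each subject as" Q2/(Q2+Q4) multiplied by 100. Presenteeism is Q5/10 multiplied by 100.

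Protocol section 7.2 describes the overall score as the two components combined and fixes the scale: "Scores for WPAI range from 0% ('no impairment') to 100% ('total loss of work productivity/activity").

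The mean total percentage of work impairment is listed among the secondary endpoints (Protocol 10.1.1; SAP 5.2, Health economics). Protocol 10.3 summarises it by IBD type and by disease activity. SAP section 8, item 5, adds a t-test or Mann-Whitney comparison of patients with moderate to severe activity against those with mild or no activity. SAP section 7.6 repeats the verbal definition, but the formula that follows it is redacted.

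**The concern.** A score that combines absenteeism and presenteeism as a percentage must count lost hours on the same scale as lost productivity. In the printed formula the multiplier sits outside the square bracket, and the bracket holds only the presenteeism part. By ordinary operator precedence the absenteeism part is never multiplied by 100. The formula therefore contradicts the definition printed directly above it.

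If the line were copied into a program, absenteeism would add at most 1 point to a 100-point score. The overall score could then fall far below its own absenteeism component. Every table reporting TWPI would carry the error. By its index, the SAP presents WPAI outcomes overall and by socio-demographic characteristics (Tables 22 to 25), by activity (54, 55), by biologic treatment (68, 69) and by hospitalisation (78, 79).

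**Working it through.** The documents give no numerical TWPI result, so there is no figure to reproduce. The check evaluates the formula directly.

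**Inputs.** From Protocol 10.3, the questions are "2) hours missed due to disease, 3) hours missed other reasons, 4) hours actually worked, 5) degree disease affected productivity while working". Write a = Q2/(Q2+Q4) and p = Q5/10. The values of Q2, Q4 and Q5 below are illustrative assumptions. The result depends only on a and p.

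**Two versions.** In the text available there is no operator between 1 and the fraction inside the bracket. The check restores a minus sign there and leaves the multiplier where it is printed.

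- As printed, minus restored: T₁ = a + [(1 − a) × p] × 100
- According to the verbal definition: T₂ = 100 × {a + (1 − a) × p}

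**Size of the error.** T₂ − T₁ = 100a − a = 99a. Absenteeism in percent is 100a, so the shortfall is 99% of it, whatever Q5 is.

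**Numbers.**

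| Q2, Q4, Q5 | Absenteeism (%) | T₁ | T₂ | Shortfall = 99a |
|---|---|---|---|---|
| 10, 30, 4 | 25 | 0.25 + 0.75×0.4×100 = 30.25 | 100×(0.25+0.30) = 55 | 24.75 |
| 20, 20, 0 | 50 | 0.5 + 0 = 0.5 | 50 | 49.5 |
| 20, 20, 2 | 50 | 0.5 + 0.5×0.2×100 = 10.5 | 60 | 49.5 |
| 8, 32, 3 | 20 | 0.2 + 0.8×0.3×100 = 24.2 | 44 | 19.8 |
| 30, 10, 2 | 75 | 0.75 + 0.25×0.2×100 = 5.75 | 80 | 74.25 |

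**Direction.** At fixed p, T₁ changes with a at the rate 1 − 100p. At Q5=1 this is 1 − 10 = −9, and it is more negative for larger Q5. So at any fixed Q5 of 1 or more, missing more work lowers the score. For Q5=4 and a = 0, 0.25, 0.50, 0.75:

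- T₁ = 40, 30.25, 20.5, 10.75
- T₂ = 40, 55, 70, 85

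**How often T₁ falls below absenteeism.** Over a grid with Q2+Q4 = 40 hours, Q2 from 0 to 40 and Q5 from 0 to 10, there are 41 × 11 = 451 combinations. T₁ is below the absenteeism percentage in 311 of them and T₂ in none. These are counts of possible answers, not of patients.

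**Effect on a group comparison.** Because the shortfall is proportional to absenteeism, the difference in mean T₁ between two groups equals the difference in mean T₂ minus 0.99 times the difference in mean absenteeism percentage. Suppose every patient has Q5=4, with a = 0.25 in one group and a = 0 in the other. The difference should be 55 − 40 = 15. As printed it is 30.25 − 40 = −9.75, which equals 15 − 0.99×25.

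**The case against.** The strongest objection is that the operative rule may be elsewhere and may be correct. Protocol 10.1.2 refers to the SAP for details. SAP 7.6 restates the four WPAI measures as percentages, each followed by a redacted formula, and the SAP contents list an appendix of derived variables that is not in the available text. This stands: nothing visible shows that the protocol line was programmed. But nothing visible corrects it either. SAP section 1 says the SAP was written in accordance with the amended protocol, and the clarifications in SAP section 8 do not mention this formula.

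A second objection is that the intent is clear from the wording and from the component formulas beside it, so this is a slip of notation. That also stands, and it is why the correction needs no judgement. It does not make the printed rule right.

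A third is that the line may have been damaged when the PDF was read. A reader might infer that the protocol also omits the minus sign. The documents do not support claiming that as an error, because one dropped character would explain it. The position of the multiplier is harder to explain that way: an outer pair of brackets would have to be lost, which needs two losses. That is unlikely but not excluded.

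Two further arguments should not be used. The absenteeism and TWPI formulas define different variables, so both can be computed; the conflict is between the TWPI formula and its definition. Nor does the 0–100% range expose the fault, because T₁ stays within it. What fails is the meaning of the upper anchor as total loss.

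**Conclusion.** The formula in Protocol 10.3 is wrong as printed, because it does not compute the quantity the protocol defines. With the minus sign restored, and if programmed literally, each score falls short by 99% of the patient's absenteeism percentage. The mean falls short by 99% of mean absenteeism among the patients with a score. At a fixed Q5 of 1 or more, the score moves the wrong way as absenteeism rises.

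The comparison by disease activity could be distorted, even reversed, if absenteeism differs by activity. A reader might infer that patients with active disease would be understated most. That is plausible, but the documents give no absenteeism figures by activity, so it remains an assumption. A reader might also infer that the study's results are wrong. The documents do not show this, since the SAP formula cannot be seen.

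The scope is limited. This is one of four WPAI scores, collected on Day 1 only and, for the work components, only in employed patients. It is a secondary endpoint, and the primary endpoint is untouched. The point should be corrected and confirmed; it does not threaten the study's main conclusion.

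**What to change.** In Protocol 10.3, replace the TWPI formula with

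100 × {Q2/(Q2+Q4) + [1 − Q2/(Q2+Q4)] × (Q5/10)}.

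Confirm that the formula in SAP 7.6, any entry in the derived-variables appendix and the SAS code all scale the whole sum and contain the minus sign. Add a program check that, for each patient with both an absenteeism and a TWPI score, absenteeism ≤ TWPI ≤ 100. If the code proves to follow the printed line, re-run the tables that report TWPI.

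The cost is one corrected line, one comparison with the SAP and code, and one automatic check. It needs no new data and does not affect patients.
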